## **JHM IRB - eForm A – Protocol**

- **Use the section headings to write the JHM IRB eForm A, inserting the appropriate material in each. If a section is not applicable, leave heading in and insert N/A.**
- **When submitting JHM IRB eForm A (new or revised), enter the date submitted to the field at the top of JHM IRB eForm A.**

\*\*\*\*\*

### **IMPROVE: Improving Cancer Care by Incorporating the Patient's Voice into On-treatment Symptom Management**

#### **1. Abstract**

- a. Provide no more than a one page research abstract briefly stating the problem, the research hypothesis, and the importance of the research.

Physician-reported measures are known to under report important symptoms and toxicities from therapy and their associated level of burden on patients, leading to missed opportunities for clinicians to intervene and improve treatment-related outcomes. With the advances in systemic therapy and in radiotherapy, definitive-intent radiation is increasingly being offered in concert with systemic therapy for patients with locally-advanced and for limited metastatic disease. however, these therapies are not without risk. In a systematic review of 19 randomized trials of patients with non-small cell lung cancer (NSCLC) receiving chemoradiation (chemoRT) compared to radiation alone, chemoRT improved survival but at a cost of greater toxicity (esophagitis: RR 1.8, 95% CI: 1.3-2.3; neutropenia: RR 3.53, 95% CI: 1.8-6.7; grade 3 to 4 anemia: RR 3.5, 95% CI: 1.8-6.8). Given the competing medical comorbidities and frailty of cancer patients at presentation, the potential risks with aggressive radiation, the ability to optimally understand, monitor, and manage cancer treatment toxicity is critical.

Patient-reported outcome measures (PROMs) is an umbrella term that refers to any report on a health status measure that is reported directly by the patient, without the influence of clinicians or anyone else. PROMs have been shown to more closely reflect a patient's daily health status when compared to physician-reported measures. Given the disconnect between patient and provider-assessed toxicity, PROMs can be used to more accurately and consistently characterize the detrimental impact of treatment on a patient's symptom-specific outcomes, functional well-being, and overall quality of life. For example, a French randomized trial in stage IV NSCLC patients showed a survival benefit (22.5 vs 14.9 months) when using web-based PROMs to guide follow-up vs. standard follow-up with imaging every 3 to 6 months. However, research is needed to evaluate if patient symptom reporting during treatment allows earlier and improved detection of treatment toxicity, and leads to individualized interventions which may improve the toxicity outcomes for locally-advanced and oligometastatic patients receiving definitive chemoRT.

**2. Objectives** (include all primary and secondary objectives)

- a. Primary objective:** Describe the proportion of patients with changes in physician-perception of treatment-related toxicity that result from routine physician review of PROMs reported during definitive radiotherapy.
- b. Secondary Objectives:** Describe (1) the proportion of patients with changes in the management of treatment-related symptoms and (2) the type of management changes that result from routine physician review of PROMs reported during definitive radiotherapy.

**3. Background** (briefly describe pre-clinical and clinical data, current experience with procedures, drug or device, and any other relevant information to justify the research)

[figure not shown]
Interest is growing in using PROMs as a tool for improving assessment of patients and to guide physician decision making. Historically, PROMs were used for collecting data on patients in clinical trials but such data was not shared with the physicians involved in earlier trials to guide decision making in the care of patients. Patient-physician discordance in the rating and perception of symptom burden in patients has been demonstrated in studies of cancer patients undergoing treatment. Use of PROMs by physicians may reduce this discordance and help improve overall assessment of the symptomatic burden for patients on-treatment. Recent studies have shown the feasibility and usability of PROMs in routine clinical care for cancer patients.

Snyder et al. randomized patients receiving oncological care to three different questionnaires assessing quality of life. Patients reported that utilization of PROMs improved the quality of care, improved communication with their physicians, and patients felt more in control of their care. Although not powered for this purpose, the trial also showed that participants from minority racial groups, with lower education levels, and less computer usage were more likely to rate the PROM intervention more favorably than their peers, suggesting a benefit for this intervention in addressing the needs of vulnerable populations. PROMs can also help physicians identify the symptoms that patients report as most bothersome, which can help clinicians tailor decision making approaches to create more beneficial outcomes for patients. There is less evidence to suggest that these assessments can lead to changes in management of symptoms and improved symptom burden as a result of treatment, though there have been some recent examples.

Lung cancer patients treated at Johns Hopkins currently report individual adverse on-treatment symptoms using the National Cancer Institute's Patient-Reported Outcomes version of the Common Terminology Criteria for Adverse Events (PRO-CTCAE, version 1). Our group has demonstrated the feasibility of routine real-time collection of PROMs in our clinic for lung cancer patients receiving radiation. Over time, we have been able to increase patient PROM completion rates to above 80 % (Figure 1).

This study builds on that clinical collection and review of PROMs by nurses. We propose a prospective pilot study to describe the proportion of patients with a change in their physician's assessment of their overall toxicity burden that result from routine physician review of PROMs during radiotherapy. We hypothesize that routine physician review of PROMs during on-treatment visits will (1) increase proportion of patients with an increased in their physician's assessment of their overall toxicity burden during definitive radiotherapy, and (2) correspondingly increase the proportion of patients receiving physician-directed interventions for treatment-related symptoms.

**Figure 1:** Patient PROM completion rates in the thoracic radiation oncology clinic

#### 4. Study Procedures

- a. Study design, including the sequence and timing of study procedures (distinguish research procedures from those that are part of routine care).

##### Patient Recruitment:

We will recruit eligible cancer patients who are about to begin conventional-fractionated (chemo-) radiotherapy. Patients will be informed of the study by their physician, clinic staff or research staff prior to the day of their first on-treatment visit. For patients who decide to participate, research staff or treating physicians will obtain an informed and written consent before or on the first on-treatment visit.

##### Clinician Recruitment:

The treating radiation oncologists have expressed a willingness to participate in the study and will help with patient recruitment. The radiation oncologists will be recruited at Johns Hopkins and at WellSpan Health through emails and will have differing levels of experience. Once we have received IRB approval, we will go through a formal consenting process. Physicians will have the option to decide not to participate. If a physician is willing to participate, she/he will be asked to provide written informed consent.

A participating physician may be included a co-investigator in this study. No physician co-investigator may analyze their own patient's PROM data included as a part of the study. There is no requirement that to be a co-investigator physician must also be a research participant.

##### Study Procedures:

In order to minimize the need for research-only in-person visits, telemedicine visits may be substituted for in person clinical trial visits or portions of clinical trial visits where determined to be appropriate and where determined by the investigator not to increase the participants risks. Prior to initiating telemedicine for study visits the study team will explain to the participant, what a telemedicine visit entails and confirm that the study participant is in agreement and able to proceed with this method. Telemedicine acknowledgement will be obtained in accordance with the Guidance for Use of Telemedicine in Research. In the event telemedicine is not deemed feasible, the study visit will proceed as an in-person visit. Telemedicine visits will be conducted using HIPAA compliant method approved by the Health System and within licensing restrictions.

As part of patients' routine on-treatment evaluation, patients will report: (1) their symptoms using PRO-CTCAE measures for cancer-specific symptoms during on-treatment visits, (2) the most bothersome symptom, and (3) effect of their symptoms on their perception of bother and role function in terms of interference with daily activities (**Appendix A.**) These measures should take only 5-10 minutes to complete.

\*\* After signing informed consents - Patients will be asked to complete the measures prior to seeing their physician, during each on-treatment visit. Patient Care Technicians (PCT), Clinical Ancillary Staff, or Research Staff will provide the PROM forms to the patients and assess the forms for completion of questions. If the first three options are not available, a nurse may provide the patients the form and confirm with the patients that the PROMs have been completed without reviewing the content of the forms. PROM forms will be completed on an electronic tablet. A hard-copy will be used as a back-up measure for patients if electronic devices or wireless functioning capabilities are not available at the time.

As a part of the study, treating physicians over-seeing the care of their patients will be asked to provide a global burden score. Lee et al. demonstrated the feasibility of using a global burden score to capture the provider's overall perception of the combined burden of *all* assessed symptoms, using a visual analogue scale demarcating an aggregate score from 0 to 10. This scale uses anchors at 0, 2, 4, 6, 8, and 10 for no, mild, moderate, severe, life-threatening adverse events, and death, respectively.

\*\* During weekly on-treatment visits and prior to reviewing their patient's PROMs, physicians will rate the symptom burden for each of their patients from 0 to 10 using available clinical data. Routine available clinical data include: vital signs, laboratory work, physical exam, nursing assessment, physician's clinical judgement. Then after reviewing the patient's PROMs, physicians will re-rate the patient's symptom burden and report any change in recommended interventions due to review of the PROMs. Management changes include (1) additional counseling, (2) medications/interventions changed, (3) referrals to other services, and (4) further testing/evaluation (**Appendix B**). At the end of each patient's course of radiotherapy, providers will complete a Clinician Feedback Form to answer questions regarding the impact of PROM review on overall symptom perception and management during treatment (**Appendix C**). These forms were designed to be easy to complete and will take an estimated 5 minutes per patient.

\*\*At the time of enrollment, research staff will collect pertinent patient baseline and characteristics through clinical chart review. During each on-treatment visit, research staff collect pertinent clinical and treatment variables through chart review (**Appendix D**). The research staff, if available on site, will also be available to assist patients in completing the questionnaires during scheduled visits and to address any issues or concerns patients have in completing the questionnaires.

\*\* Marks demarcates interventions that will/may require research staff availability and assistance.

- b. If your study involves data/biospecimens from participants enrolled under other research studies with a written consent or under a waiver of consent, please list the IRB application numbers for those studies. Please note: Certificate of Confidentiality (CoC) protections applied to the data in source studies funded by NIH or CDC will extend to this new study if the funding was active in 2016. If this situation applies, Section 36, question 4 in the application will need to be answered "Yes" and "Hopkins Faculty" should be selected in question 7. No other documents are required.

Not applicable.

- c. Study duration and number of study visits required of research participants.

Patients will be enrolled in the study prior to or on their first radiotherapy on-treatment visit and will continue through the course of their radiotherapy. Data will be collected at routine weekly on-treatment visits; no study-specific visits are required

d. Blinding, including justification for blinding or not blinding the trial, if applicable.

Blinding will not be possible as the treating physician will need to provide routine care to the patients enrolled on this study. In addition, the treating physician will need to appropriately assign burden scores, and to report on whether there was a change in management for each of their patients who enroll on this study.

e. Justification of why participants will not receive routine care or will have current therapy stopped.

Patients will continue to receive their routine care. This study will not alter nor stop the planned radiotherapy treatments. All patients enrolled will undergo routine weekly on-treatment evaluation and toxicity management by the treating physician.

f. Justification for inclusion of a placebo or non-treatment group.

There is NO placebo group. This is a pilot study to evaluate whether physician review of PROMs during radiotherapy changes the physician's assessment of a cancer patient's overall toxicity burden and management of treatment-related symptoms. There is insufficient sample size to include a placebo group. In future studies building on this, where we have a greater sample size, we can randomize patients to 2 arms: with and without routine PROM review.

g. Definition of treatment failure or participant removal criteria.

Patients will be removed if they desire to refrain from answering the PROM questionnaire.

h. Description of what happens to participants receiving therapy when study ends or if a participant's participation in the study ends prematurely.

There will be no change in the patient's routine care or treatment.

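### The burden score taken before PROM review may draw on the nursing assessment, and no rule keeps PROM content out of that assessment before the first rating

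*Combined protocol and SAP*

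**What the plan says.** Section 4 (Study Procedures) sets the order of the two ratings. At weekly visits, "prior to reviewing their patient's PROMs, physicians will rate the symptom burden for each of their patients from 0 to 10 using available clinical data". The inputs to that first score are then listed: "vital signs, laboratory work, physical exam, nursing assessment", and the physician's own judgement. After reading the PROMs the physician scores again and notes any resulting change in management.

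Three other statements bear on what the nursing assessment may contain.

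- Section 3 (Background), after describing routine PROM collection in the lung cancer clinic: "This study builds on that clinical collection and review of PROMs by nurses".
- Section 4, on timing: "Patients will be asked to complete the measures prior to seeing their physician, during each on-treatment visit". The completed form therefore exists before the physician's first score.
- Section 4e: "Patients will continue to receive their routine care".

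The one safeguard is also in Section 4. Technicians, ancillary staff or research staff hand out the forms. If none is available a nurse may do so, and is to "confirm with the patients that the PROMs have been completed without reviewing the content of the forms".

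Section 7a defines the primary outcome as the proportion of patients whose score changes at one or more visits. Section 7b defines the secondary outcome in the same way for management.

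**The concern.** The design isolates the effect of PROM review by comparing two scores given by the same physician at the same visit. That works only if the first score is free of PROM content. If a nurse has read the day's form and its content enters the nursing assessment, some of the PROM information is already in the first score. The second score then has less room to move, and the change is not counted. The secondary outcome is exposed in the same way: an intervention prompted by what the nurse relayed may already be in the physician's plan before PROM review.

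The associations by treating physician planned in Section 7c could also partly reflect how nurses work with each physician. If exposure is not recorded at the visit, it cannot be reliably reconstructed later.

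**Working it through.** **1. Is the pathway closed anywhere?** The nursing assessment is a permitted input to the first score. Nurse review is described as existing practice. The form is complete before the physician is seen, and routine care continues. The instruction not to read content applies to a nurse distributing forms as a fallback. Nothing in the text supplied extends it to other nurses, requires the nursing assessment to come before the form, or withholds PROM-derived content from the physician until the first score. The pathway is open.

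**2. The plan's own precision figure.** Section 7d gives a width below 30% (±15%) for at least 50 patients. The exact 95% interval at 25/50 is 35.5% to 64.5%, a width of 28.9%, the maximum over all outcomes. The largest one-sided half-width is 14.8%. The stated figure reproduces. Contamination would move the estimate and leave this formula unchanged.

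**3. Illustrative size of the pathway alone.** Inputs from Section 7d: 5 to 7 weeks of treatment, taken as 6 weekly visits, and PROM completion above 80% of visits (reported for lung cancer patients), taken as 0.8. Assumptions not in the documents: *p*, the chance that PROM review changes the score at a reviewed visit; *c*, the share of visits where PROM content arrives first; full absorption at those visits; independent visits.

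Proportion ever changed = 1 − (1 − 0.8·*p*·(1 − *c*))^6

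| *p* | *c* = 0 | *c* = 0.25 | *c* = 0.50 |
|---|---|---|---|
| 0.20 | 1 − 0.84^6 = 64.9% | 1 − 0.88^6 = 53.6% | 1 − 0.92^6 = 39.4% |
| 0.30 | 1 − 0.76^6 = 80.7% | 1 − 0.82^6 = 69.6% | 1 − 0.88^6 = 53.6% |

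The loss is about 11 points at *c* = 0.25, inside the 15-point margin. At *c* = 0.50 it is 25.5 points (*p* = 0.20) or 27.2 points (*p* = 0.30), outside it. Partial absorption would give smaller losses.

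**4. Net direction.** A re-rating can also change for reasons unrelated to the PROMs, at a rate *s* per visit, and any such change counts. Let *q* be the chance per visit of a PROM-driven change. The observed proportion is 1 − [(1 − *q*(1 − *c*))(1 − *s*)]^6. With *q* = 0.10 the uncontaminated PROM-driven proportion is 1 − 0.90^6 = 46.9%. The net shift in points from that value is:

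| *c* | *s* = 0.02 | *s* = 0.05 | *s* = 0.10 |
|---|---|---|---|
| 0.25 | −2.3 | +7.1 | +19.9 |
| 0.50 | −12.0 | −0.9 | +14.1 |

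The sign depends on rates that the documents do not give.

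**5. Would dropping affected visits repair the primary proportion?** Under the model in step 3, affected visits produce no changes, so removing them removes no changed patients. At *p* = 0.20 and *c* = 0.50 the result stays at 39.4%. If patients with no clean visit leave the denominator, it is 0.394 / (1 − 0.5^6) = 40.0%. Neither figure approaches 64.9%. The per-visit rate is informative: under the same model it is 20% at clean reviewed visits and 0% at affected ones.

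**The case against.** The strongest defence concerns the comparator. Section 3 presents the study as building on nurse review and Section 4e keeps routine care in place. The question could therefore be what physician review adds to usual care that already includes nurse review. On that reading a nurse-informed first score belongs to the comparator and is not bias. The reading is tenable, but the plan never states it. The objective in Section 2 concerns change resulting from physician review, and Section 4f looks ahead to a trial with and without routine PROM review. Either way, the reader needs to know what the first score contained.

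The fallback clause can also be read as a sign that nurses were meant to stay unaware of PROM content. That is an inference from one clause, and the clause does not reach nurses who are not handing out forms.

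Three stronger conclusions are tempting and unsupported:

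- *That contamination occurs.* No text says nurses read that day's form before the first score or pass its content on. A nurse's summary may also be partial, leaving room for the score to move after full PROM review.
- *That the primary outcome is biased toward no change overall.* The same unblinded physician rates twice, and one change at any visit is enough, which pushes the proportion upward. Only this single pathway has a known direction.
- *That the two institutions differ.* Section 4 (Clinician Recruitment) names WellSpan Health as a second source of physicians, but nurse workflow there is not described.

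**Conclusion.** The gap holds as a weakness in procedure: a physician following Section 4 as written can have PROM content in the score meant to precede PROM review. That pathway alone reduces observed change in both the primary and the secondary outcome. Its frequency, any difference between sites and the net bias are unknown from the documents.

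The fall from 65% to 54% or 39% shows that the effect could be small or could exceed the planned margin. It is not an estimate, because it rests on assumed rates, full absorption and independent visits. For a descriptive pilot this does not threaten the study. It merits correction because the before/after contrast is the study's only comparison and protecting it costs very little.

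**What to change.** 1. **Ordering rule.** Add to Section 4: the first burden score is recorded before the physician receives any PROM-derived information, including through the nursing assessment. If usual care with nurse review is the intended comparator, say so instead and word the conclusion as the added effect of physician review.
2. **Record of exposure.** Add one tick box to the weekly form: *PROM content already known before first rating (yes/no)*. Appendix B is not in the text supplied, so add this only if it has no such item.
3. **Reporting.** Keep the primary analysis unchanged. Beside it, give the per-visit proportion of score changes separately for 'no' and 'yes' visits, and by site. Read the contrast descriptively, since the two kinds of visit may differ in other ways. Do not recompute the patient-level proportion after dropping visits: discarding visits cannot restore lost changes and can only remove patients from the 'ever changed' count.

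Cost: a sentence or two, one tick box, one extra table and a few seconds per visit, with no added staff. One limit remains: physicians may not always recognise which part of a nursing assessment came from the PROM, so the tick box may under-record exposure.

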**7. Study Statistics**

This is a prospective pilot study.

- a. Primary outcome variable(s).

*The primary outcome is the proportion of patients with any change in their physician-assessed burden scores for at least one on-treatment visit, along with their exact binomial 95% confidence interval.*

- b. Secondary outcome variables

*The secondary outcome is the proportion of patients with a change in their on-treatment management for at least one on-treatment visit, along with the exact binomial 95% confidence interval.*

- c. Exploratory outcome variables:

We will also summarize the mean change in the physician-assessed burden score across on-treatment-visits, and across patients, using mean, standard deviation, median and ranges. We will report the distribution of changes (an increase, decrease or no change) in physician burden score after PROM review across all visits.

We will also summarize the mean change in the physician interventions across on-treatment-visits, and across patients, using mean, standard deviation, median and range of cumulative changes in interventions made. We will explore the average cumulative number of management interventions based on each specified numerical change in burden score.

*Additionally, we will describe differences in mean physician burden score between first half and second half of treatment.* To describe changes in the physician perception of treatment-related toxicity resulting from routine physician review of PROMs, we also will compare the mean change in burden scores for on-treatment visits 4 to 7 to the mean change in burden scores for visits 1 to 3. Treatment-related toxicities are expected to worsen over time. If PROM review does not change physician perception of treatment-related symptoms, there would no difference between the mean change in burden score across patients in the first half of treatment compared to the second half of treatments. Using paired t-tests, we will examine the differences between mean physician burden score across patients in the second compared to the first half of the treatments. We would expect the changes in burden scores to be greater in later visits since treatment-related toxicities and corresponding PROMS are expected to worsen over time.

*Depending on the proportion of patients with a change in physician burden assessment, we will also explore potential variables associated with a change in burden assessment by the physician.*

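### Management change is described only as a post-review change the physician credits to the PROMs, with no pre-review record of intended management in the procedures text

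*Combined protocol and SAP*

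**What the plan says.** Section 4a sets the order of events at each weekly visit. Before opening the PROMs, "physicians will rate the symptom burden for each of their patients from 0 to 10 using available clinical data". After reading them, the physician scores burden again and is to "report any change in recommended interventions due to review of the PROMs". Four kinds of management change are listed (counseling, medications or interventions, referrals, testing or evaluation), with Appendix B cited as the form.

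Section 4d confirms that the treating physician is unblinded and is to "report on whether there was a change in management for each of their patients who enroll on this study". Section 4f rules out a comparison group: "There is insufficient sample size to include a placebo group".

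Section 2 makes the secondary objective causal in wording, including "the type of management changes that result from routine physician review of PROMs". Section 7b defines the outcome as "the proportion of patients with a change in their on-treatment management for at least one on-treatment visit", "along with the exact binomial 95% confidence interval".

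Two other sources touch on management. "During each on-treatment visit, research staff collect pertinent clinical and treatment variables through chart review" (Appendix D), but the text gives this review no role in checking attribution. The Clinician Feedback Form (Appendix C), completed at the end of each course, asks the physician about the effect of PROM review on symptom perception and management; section 7d plans to explore its ratings.

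**The concern.** Burden change is the difference between two recorded values. Management change, as described, is a single judgement made after the PROMs have been read, by the person whose behaviour is being studied, against a plan that the text does not say is written down.

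Two errors are possible. The physician may credit the PROMs with an action that would have been taken anyway, which raises the proportion. Or the physician may not credit the PROMs with an action they did prompt, which lowers it. Nothing in the protocol ranks the two.

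A patient counts after one positive visit, so false credits accumulate over the course of treatment. The planned interval covers sampling error only. The same weakness carries into the breakdown by type of change and into the exploratory tables and plots that relate interventions to burden scores. A pre-review plan that was never recorded cannot be reliably reconstructed later.

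**Working it through.** **Side by side (section 4a).**
- Burden: recorded before review and after review; change is derived.
- Management: nothing described before review; after review, a reported change with its cause attributed.
- Appendix C: physician self-report at the end of the course; it supplies no before record.
- Appendix D chart review: not described as capturing the plan before review.

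**The plan's own precision figure.** The exact (Clopper-Pearson) 95% interval for 25 of 50 is 35.5% to 64.5%, a width of 28.9 points. The largest distance from estimate to limit over all outcomes is 14.8 points. The statement in section 7d (width under 30%, ±15%) is correct and is not disputed.

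**Illustration of size.** From section 7d: 5-7 weeks of treatment, so k = 5, 6 or 7 weekly visits; PROM completion 80% (the text gives more than 80%, for lung patients only); n = 50. Assumed, and found nowhere in the documents: true patient-level proportion T; false credit f at 2% or 5% of visits with a PROM; missed credit m for 10% or 25% of true changes; independent visits, or within-patient correlation 0.2.

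*Upward shift*, independent visits: (1 − T) × [1 − (1 − 0.8f)^k].
- T = 0.50, f = 0.02, k = 5: 0.5 × (1 − 0.984^5) = 0.039.
- T = 0.50, f = 0.05, k = 7: 0.5 × (1 − 0.96^7) = 0.124.
- T = 0.30, f = 0.05, k = 5/6/7: 0.7 × (1 − 0.96^k) = 0.129/0.152/0.174.

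For correlation 0.2, a beta-binomial replaces (1 − 0.8f)^k with B(a, b + k)/B(a, b), where a = 4 × 0.8f and b = 4 × (1 − 0.8f). At T = 0.50 the shift is then 0.028 to 0.081. At T = 0.30, f = 0.05, k = 7 it is 0.114.

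*Downward shift*, independent visits: p = 1 − (1 − T)^(1/k), and shift = 1 − [1 − (1 − m)p]^k − T.
- T = 0.50 gives p = 0.129/0.109/0.094 for k = 5/6/7.
- m = 0.10: −0.038 for each k.
- m = 0.25: −0.100/−0.099/−0.099.

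With correlation 0.2 (simulated, mean set so that T = 0.50) the range is −0.024 to −0.073.

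*Both errors*, T = 0.50, independent visits: 1 − [1 − (1 − m)p]^k × (1 − 0.8f)^k − 0.50. This runs from −0.054 (f = 0.02, m = 0.25, k = 5) to +0.096 (f = 0.05, m = 0.10, k = 7).

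*Other true proportions*, over both correlation settings: at T = 0.30, up 0.039 to 0.174 and down 0.017 to 0.067; at T = 0.70, up 0.017 to 0.075 and down 0.025 to 0.117.

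**Coverage of a true 50% by the exact 95% interval, n = 50.**

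| Probability that a patient is recorded as changed | Coverage |
|---|---|
| 0.50 (no error) | 96.7% |
| 0.528 | 95.3% |
| 0.462 | 94.1% |
| 0.40 | 76.3% |
| 0.6245 | 64.1% |

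The last two rows use the largest one-directional errors with independent visits.

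**The case against.** Physician attribution is the disclosed measure. The procedures say so, section 4f explains the lack of a comparison group and points to a future randomized study, and section 7d calls the analyses descriptive. The physician must also commit to a burden score, using examination, laboratory results and nursing assessment, before opening the PROMs, and the management report belongs to the same visit sequence. That limits recall error. All of this stands, and it keeps the point modest. It does not supply a recorded plan, and the objective is still worded as change resulting from review.

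Appendix B is the form for this very item and is not reproduced. A reader might infer that the study has no before record at all. The text does not support that: the form may contain the field, and only the procedures text can be judged.

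A reader might also infer that the proportion will be inflated, or that bias will swamp the interval. Neither is supported. Both directions are plausible, and every error rate above is assumed. At a true 50% none of the shifts reaches 15 points. At a true 30% a single-direction shift exceeds 15 only with the highest false-credit rate, independent visits and 6 or 7 visits.

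Finally, simply replacing the outcome with any difference between two records would count changes arising from conversation or second thoughts. That objection is right, and the fix below keeps the attribution item for this reason.

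**Conclusion.** The point holds for what the procedures text describes, subject to confirmation against Appendix B. The secondary proportion and the breakdown by type of change rest on one unblinded physician's attribution against a plan not described as recorded. The direction and size of the error are unknown. Under the assumed rates it is a few points to about 12 at a true 50%, and up to about 17 at a true 30%, which is beyond the stated ±15 margin. These figures show what is possible, not what is likely.

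The scope is a secondary outcome in a descriptive pilot. The primary outcome does not share the missing-record problem, since burden is scored twice. A reader might conclude that it is therefore free of bias. It is not: the same unblinded physician gives both scores knowing that PROM review falls between them, so expectation effects apply there too.

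**What to change.** First check Appendix B. If it already has a pre-review management field, say so in section 4a and define the outcome from it. If not:

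1. With the first burden score, before opening the PROMs, the physician ticks intended management in the existing four categories.
2. After review the physician ticks the same categories again, with an added box for same category, content changed. The box is needed because extra counseling, for example, would otherwise not show when counseling was already ticked.
3. Keep the item asking whether a change was due to the PROMs.
4. In section 7b, count as PROM-related a change that differs between the two records (or has the content box ticked) and is attributed to the PROMs. Report the any-difference and attribution-only proportions beside it.

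If the form cannot be changed, report the result as physician-attributed management changes and do not state it as changes that result from PROM review.

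The cost is a form revision, a protocol amendment and slightly more physician time per visit, on top of the estimated 5 minutes per patient; no added visits or staff. The proportion may come out lower than under attribution alone. The same unblinded physician completes both records, and the content box is still self-report, so bias is reduced but not removed.
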